2.6.2.6 Rescue medication

The number of puffs of rescue medication during the past 12 hours is recorded twice (morning/evening) by the patient in the e-Diary. The baseline values are defined as the average from all non-missing records taken over the last 14 days of the run-in period between run-in Visit 101 and up to one day before first dose of study drug.

The mean daily number of puffs of rescue medication use will be calculated for each patient over the first 26 weeks, over the whole 52 weeks of double-blind treatment, and over 4 weekly intervals as described for other data of the e-Diary. This will be done separately for morning (night-time), evening (daytime), and daily (night-time plus daytime) rescue medication use. Similar ANCOVA and MMRM as used for the analysis of PEF with baseline PEF value replaced with the appropriate baseline mean number of puffs.

The percentage of 'rescue medication free days' (defined as any day where the patient did not use any puffs of rescue medication during daytime and night-time) will be summarized by treatment and analyzed in the same way as described for the number of puffs of rescue medication use with baseline mean number of puffs replaced with the baseline percentage of rescue medication free days as a covariate. In case of non-convergence or evidence of highly skewed data, non-parametric tests such as Wilcoxon Rank Sum Test will be explored.

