16.1.9.3.2 Baseline measurements

In general, baseline is defined as the last measurement before the first dose of study drug at Day 1.

1) For all **FEV₁, FVC, and FEF₂₅₋₇₅** endpoints, the baseline value is defined as the average of the values taken at -45 and -15 min prior to first dose of study drug at the evening of Day 1. Checks will be performed to ensure both values were indeed taken prior to the first dose of study drug. If one of the -45 and -15 min values is missing (or is not confirmed to be pre-dose) then the remaining non-missing value will be taken as the baseline. If both values are missing (or not confirmed to be pre-dose), then the last out of the pre-bronchodilator measurements taken at the run-in Visits 101 and 102 or at unscheduled run-in visits will be used as the baseline. If the FEV₁, FVC or FEF₂₅₋₇₅ measurements are missing both on Day 1 and at run-in visits, the respective baseline values will be set to missing. Measurements taken within 6 hours of rescue use, and/or within 7 days of systemic corticosteroid use, and/or 3 months of single depot corticosteroid injection, will be set to missing.

For all baseline spirometry measurements, we exclude the implausible values. Specifically, if a patient has implausible FEV₁ value (defined as > 7 L) at baseline assessment, all spirometry measurements related to that assessment will be excluded.

2) For the **ACQ** scores, the baseline value is defined as the score obtained at Day 1 (V102). If the value is missing, the last measurements from run-in visit 101 or unscheduled run-in visits will be used.

3) For patient **diary data (PEF, symptoms, and rescue medication use)**, the baseline values are defined as the average from all non-missing records taken in the run-in period over 14 days from Visit 101 up to one day before first dose of study drug (i.e., from Day -14 to Day -1 inclusively). Missing diary data will not be imputed.

Baseline PEF will be calculated separately for morning and evening values.

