The night-time symptom score consists of one question 'How did you sleep last night?' which has to be answered with scores from 0 = 'I did not wake up because of any breathing problems.' up to 4 = 'I had difficulty sleeping because of my breathing problems even though I used my rescue medication.' The morning score consists of the question 'Did you have asthma symptoms upon awakening in the morning?' which has to be answered with scores from 0 = 'None' up to 4 = 'Very Severe'. There are 5 questions including the today's severity of shortness of breath, wheeze, cough, and chest tightness during the past 12 hours, and 'Did your respiratory symptoms stop you from performing your usual daily activities?' which are part of the daytime symptom score. All have to be answered with a score from 0 = 'None / Not at all' up to 4 = 'Very Severe / Completely'. The average of the 5 scores is defined as the daytime symptom score. The baseline scores will be derived by averaging over the days of the run-in period with non-missing data, separately for each score, the night-time, morning, and daytime symptom score.

The baseline total daily symptom score will be obtained in the first step by adding the night-time symptom score, the morning score, and the mean daytime symptom score for each single day. In the second step, these daily symptom scores will be averaged over the days of the run-in period with non-missing data. The score is in the range from 0 to 12. For the derivation of the total daily symptom score, all 3 scores have to be available at that day. Otherwise a total daily symptom score will not be calculated for that day.

Rescue medication use will be analyzed separately for the number of puffs during daytime, night-time, and over the complete 24 hours. Baseline is defined as the average number of puffs per day in the run-in period. If for the value over the whole day (24 hours) the number of puffs is missing for part of the day (either day-time or night-time) then a half day will be used in the denominator to calculate the average value. Any values > 30 for the number of puffs of rescue medication in a 12 hour period will be set to missing. These high numbers are not realistic and could impact the analyses.

If a patient has less than 7 days with non-missing data, then the respective baseline value will be set to missing.

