For **diary data (PEF, symptom scores and rescue medication use)**, post-baseline measurements start with the morning recordings at Day 2 and end with the evening recordings one day after the last evening dose. Summary data (i.e., mean values and percentage of days with) will be calculated for 4-weekly intervals (defined as 28 days), for Weeks 1 – 26 (defined up to Visit 207, Day 183), and for Weeks 1 – 52 (defined as the whole treatment period up to Visit 214, Day 365). Similar calculations as for baseline diary data will be done. If there will be less than 14 days with data in a 4-week period, then the data should collapse with the previous 4-week period. For Weeks 1 – 26 and 1 – 52, summary values will only be calculated if a patient has at least 30% of their diary days and at least 20 diary days with evaluable data for that variable in the period of interest.

For **safety data**, post-baseline measurements comprise recordings up to the last dose of study drug + 7 days for laboratory, ECG, vital signs, non-serious AE and up to the last dose of study drug + 30 days for SAEs and death. ECG, vital signs and laboratory values which have complete date and time values are assigned to pre or post-dose assessment based on the actual date/time. However, values with missing date/time are assigned to their respective scheduled visit date and time given the visit number and time point are non-missing. If a measurement scheduled as

pre-dose is actually performed post-dose, or vice versa, the data will not be used for by time point assessments but will be included in the summaries of the notable values and extreme values.

When change from baseline is of interest the following formula will be used for each scheduled visit and time-point where baseline and post-baseline values are both available:

Change from baseline = post-baseline value – baseline value.

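### The half-day denominator biases mean daily rescue use when day and night use differ and unequal numbers of day and night entries are missing; summing the two half-day means avoids this

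*SAP*

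**What the plan says.** Patients enter puff counts twice a day. SAP 2.6.2.6: "The number of puffs of rescue medication during the past 12 hours is recorded twice (morning/evening) by the patient in the e-Diary". The morning entry covers the night and the evening entry covers the day. The same section derives three summaries: night-time, daytime and "daily (night-time plus daytime) rescue medication use". SAP 16.1.9.3.2 repeats the split: "Rescue medication use will be analyzed separately for the number of puffs during daytime, night-time, and over the complete 24 hours".

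The baseline window runs "from Day -14 to Day -1 inclusively", and for rescue use "Baseline is defined as the average number of puffs per day in the run-in period". If one of a day's two counts is missing, "then a half day will be used in the denominator to calculate the average value". The same section states "Missing diary data will not be imputed". It sets 12-hour counts above 30 to missing and requires at least 7 days with data.

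For on-treatment summaries, SAP 16.1.9.3.3 says "Similar calculations as for baseline diary data will be done". It adds a 14-day minimum for each 4-week interval, and minima of 30% of diary days and 20 days for Weeks 1–26 and 1–52. The SAP gives no reason for the half-day rule and plans no sensitivity analysis of it.

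**The concern.** Daily use is defined as a sum of two parts, but the rule estimates it as twice the average over whichever half-days were recorded. If a patient uses the inhaler more by day and skips evening entries more often, heavy-use half-days drop out of numerator and denominator together, and the mean drifts towards the night-time rate. The reported 24-hour mean then no longer equals the sum of the daytime and night-time means that the SAP reports beside it.

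At stake is mean daily rescue use over 26 and 52 weeks, a listed secondary endpoint (SAP 2.1.3). It is compared between arms by ANCOVA and MMRM with its own baseline as covariate.

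**Working it through.** **Inputs.** From the SAP: two 12-hour entries per day; a 14-day baseline window; a day with one entry counts 0.5 in the denominator; daily use is day plus night. The documents give no puff rates, no diary missingness and no figure for this rule, so there is no stated result to reproduce. All rates below are assumptions.

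**Step 1: the rule as a formula.** Let nD and nN be the recorded daytime (evening-entry) and night-time (morning-entry) counts for a patient, and mD and mN the mean puffs per entry. Full days count 1 and half-recorded days 0.5, so the denominator is (nD + nN)/2:

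R = (nD·mD + nN·mN) / [(nD + nN)/2]

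The target is S = mD + mN.

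**Step 2: the error.**

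R − S = [2nD·mD + 2nN·mN − (nD + nN)(mD + mN)] / (nD + nN) = [(nD − nN)/(nD + nN)] × (mD − mN)

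This is a product of two terms: the imbalance in recorded entries and the day–night gap in use. If either is zero, the error is zero.

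**Step 3: size under assumed rates.**

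| Puffs day/night | Evening / morning entries missing | Rule | Target | Error |
|---|---|---|---|---|
| 1.5 / 0.5 | 20% / 0% | (0.8×1.5 + 1.0×0.5)/0.9 = 1.889 | 2.00 | −5.6% |
| 1.5 / 0.5 | 20% / 15% | (0.8×1.5 + 0.85×0.5)/0.825 = 1.970 | 2.00 | −1.5% |
| 2.0 / 0.5 | 30% / 0% | (0.7×2.0 + 1.0×0.5)/0.85 = 2.235 | 2.50 | −10.6% |
| 2.0 / 0.5 | 30% / 25% | (0.7×2.0 + 0.75×0.5)/0.725 = 2.448 | 2.50 | −2.1% |
| any | equal | equals target | – | 0 |

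The sign reverses when night entries are the ones missing. With 3 and 1 puffs, 14 day and 10 night entries give (42 + 10)/12 = 4.33 against 4.00; 12 and 12 entries give exactly 4.00.

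**Step 4: the treatment difference.** Write d for the imbalance term and g for the gap. The error in the difference between two arms is d1·g1 − d0·g0. With 14 day and 10 night entries in both arms, d = 4/24 = 1/6:

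- 3/1 against 2/1 puffs: 3.17 − 4.33 = −1.17, where the truth is −1.00.
- 3/1 against 2.5/0.5 puffs (same gap): 3.33 − 4.33 = −1.00, no error.

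**Step 5: simulation.** Poisson counts at 3/1 puffs, 14 days, 100,000 patients, entries missing completely at random:

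| Day / night missing | Error of rule | Error of sum of means |
|---|---|---|
| 10% / 10% | 0.00 | 0.00 |
| 20% / 20% | 0.00 | 0.00 |
| 5% / 20% | +0.18 | 0.00 |
| 10% / 30% | +0.26 | 0.00 |
| 20% / 5% | −0.18 | 0.00 |

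The sum of means stayed within about 0.003 of zero. When night entries were missing more often on nights without use (30% against 5%), the sum of means was off by +0.10 and the rule by +0.25.

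**Step 6: another reading.** If the rule means doubling each half-recorded day and averaging over days, four missing nights of 14 give (10×4 + 4×6)/14 = 4.57 against 4.00. Two missing days and two missing nights give (10×4 + 2×6 + 2×2)/14 = 4.00. The same two conditions apply.

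**The case against.** The half-day rule is pre-specified, uses every recorded entry, and is exact when the two halves are missing equally often. Nothing in the documents shows that they are not. Both entries sit on one twice-daily device, reviewed at each clinic visit (Protocol 6.4.3). Patients unwilling to complete it are excluded (Protocol 4.2, criterion 29), and sites check completion by telephone (Protocol Table 6-1, footnote 5). With 20% and 15% missing rather than 20% and 0%, the error falls to −1.5%. Daytime and night-time use are also analysed separately without the rule, so a discrepancy would be visible. All of this stands and keeps the point minor. Unequal missingness is still plausible: the evening diary has seven items against four in the morning (Protocol Appendix 8).

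A reader might infer more than the plan supports:

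- *That the rule is biased whenever day and night use differ.* It is not; the imbalance term must also be non-zero.
- *That the error scales the arm means and the treatment difference.* It is additive, and cancels between arms with the same gap and the same imbalance.
- *That any difference in diary compliance between arms matters.* An arm with poorer but balanced completion has no error; only the day-against-night imbalance counts.
- *That error in the baseline covariate biases the comparison.* Baseline is recorded before the first dose, so in a randomised comparison it costs precision rather than introducing bias in expectation. The on-treatment use of the rule is what matters.

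**Conclusion.** The point holds in a limited form. The 24-hour mean departs from the SAP's own definition of daily use only when day and night use differ and unequal numbers of day and night entries are missing. The treatment difference is biased only if the arms differ in the day–night gap or in the missingness imbalance.

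In the assumed scenarios of Step 3 the error runs from zero to about −11%. The larger values depend on one-sided missingness that the documents neither report nor rule out. The conclusion also takes the post-baseline reference to similar calculations as including the half-day rule.

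The endpoint is secondary and tested at nominal level outside the family of three hypotheses (SAP 2.6.1.3). Primary and key secondary conclusions are unaffected. This is a low-cost refinement, not a flaw that threatens the trial.

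**What to change.** In SAP 16.1.9.3.2, with a cross-reference in 16.1.9.3.3, replace the half-day denominator with wording such as: *mean daily rescue use for a patient and period is the mean of the available daytime counts plus the mean of the available night-time counts.* Both components are already derived.

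Apply the existing minimum-data rules to each half: 7 days at baseline; 14 days per 4-week interval, collapsing both halves together if either falls short; and 30% and 20 days for Weeks 1–26 and 1–52. Without this, one night entry beside 14 day entries would fix the whole night component.

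**Cost.** A short SAP edit and a few more missing values. A patient with no night entries at all would have no 24-hour value, where the unmodified averaging rule would return 6.0 at true rates of 3 and 1. The sum is noisier when one half has few entries. In the Step 5 simulations the difference in spread was small: in the 20%/5% case the standard deviation was 0.593 for the sum and 0.581 for the rule, and with unequal missingness the other way (5%/20%) it was 0.564 and 0.605. The change removes the weighting error only; bias from informative missingness remains.

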16.1.9.3.3 Post-baseline measurements

Post-baseline measurements are defined as those assessments after the first dose of study drug.

FEV₁, FVC and FEF₂₅₋₇₅ measurements taken within 6 hours of rescue use or within 7 days of systemic corticosteroid use or within 3 months of single depot corticosteroid injection will be set to missing. The trough value is defined as the average of the two measurements taken 23 hr 15 min and 23 hr 45 min post-evening dose. If the actual measurement times will be outside of the 22 - 25 hour post-evening dose time window for o.d. regimens (or outside the 8 - 13 hour post-morning dose time window for b.i.d. regimens), then the individual value will be set to missing. If one of the two values is missing (or set to missing) then the remaining non-missing value will be taken as the trough value. If both values are missing, then the trough value will be missing. In a similar way pre-dose trough is defined as the average of the two measurements taken 45 min and 15 min pre-evening dose. Pre-dose measurements will be set to missing when they are actually taken post-dose. However, the post-evening dose time window of 22 – 25 hours or the post-morning dose time window of 8 – 13 hours for b.i.d. regimens can not be applied here since the dosing data of the previous day or the morning of the day of pre-dose measurements will not be recorded. If one of the -45 and -15 min values is missing (or is not confirmed to be pre-dose) then the remaining non-missing value will be used as average pre-dose value.

Post-dose spirometry measurements (i.e., at 5, 15, 30, 60 min) which were actually taken pre-dose will be set to missing and not used for by time point assessments.

For all post-baseline spirometry measurements, we exclude the implausible values. Specifically, if a patient has implausible FEV₁ value (defined as > 7 L) at an assessment, all spirometry measurements related to that assessment will be excluded.

For **diary data (PEF, symptom scores and rescue medication use)**, post-baseline measurements start with the morning recordings at Day 2 and end with the evening recordings one day after the last evening dose. Summary data (i.e., mean values and percentage of days with) will be calculated for 4-weekly intervals (defined as 28 days), for Weeks 1 – 26 (defined up to Visit 207, Day 183), and for Weeks 1 – 52 (defined as the whole treatment period up to Visit 214, Day 365). Similar calculations as for baseline diary data will be done. If there will be less than 14 days with data in a 4-week period, then the data should collapse with the previous 4-week period. For Weeks 1 – 26 and 1 – 52, summary values will only be calculated if a patient has at least 30% of their diary days and at least 20 diary days with evaluable data for that variable in the period of interest.

For **safety data**, post-baseline measurements comprise recordings up to the last dose of study drug + 7 days for laboratory, ECG, vital signs, non-serious AE and up to the last dose of study drug + 30 days for SAEs and death. ECG, vital signs and laboratory values which have complete date and time values are assigned to pre or post-dose assessment based on the actual date/time. However, values with missing date/time are assigned to their respective scheduled visit date and time given the visit number and time point are non-missing. If a measurement scheduled as

pre-dose is actually performed post-dose, or vice versa, the data will not be used for by time point assessments but will be included in the summaries of the notable values and extreme values.

When change from baseline is of interest the following formula will be used for each scheduled visit and time-point where baseline and post-baseline values are both available:

Change from baseline = post-baseline value – baseline value.

16.1.9.4 Laboratory parameters – direction of interest and definition of clinically notable values

The following table shows the direction of interest when analyzing worst case values in form of maximum and/or minimum post-baseline values. If the direction of interest is given as "High" the maximum value will be calculated and used as worst value, if the direction is given as "Low" the minimum value will be taken, and if it is given as "Low and high", both the minimum value and the maximum value will be calculated and presented in summary tables.

Direction of interest for worst case value for laboratory parameters

Laboratory Parameter	Direction of interest for worst case value
A. Hematology	
Hemoglobin	Low
Hematocrit	Low
Erythrocytes	Low
Leukocytes	Low and high
Basophils	High
██████████	██████████
Lymphocytes	Low and high
Monocytes	High
Neutrophils	Low and high
Platelets	Low and high
B. Chemistry	
Albumin	Low
Alkaline Phosphatase	High
ALT/SGPT	High
AST/SGOT	High
Bilirubin Total	High
Blood Urea Nitrogen (BUN)	High
Creatinine	High
Glucose	Low and high
Gamma GT	High
Potassium	Low and high
Magnesium	Low and high
Uric acid	High
Plasma cortisol	Low and high

The following table shows the criteria for clinically notable laboratory values. Not all parameters have notable criteria defined.

Clinical notable criteria for selected laboratory tests

Laboratory parameter (unit)	Lower bound of clinically notable range	Upper bound of clinically notable range
Hematology		
Hematocrit (v/v)		
Male	0.37	-
Female	0.32	-
Hemoglobin (g/L)		
Male	115	-
Female	95	-
Platelets (x10 ⁹ /L)	75	700
Leukocytes (x10 ⁹ /L)	2.8	16.0
Chemistry		
Albumin (g/L)	25	-
Alkaline Phosphatase (U/L)	-	3 x ULN
ALT/SGPT (U/L)	-	3 x ULN
AST/SGOT (U/L)	-	3 x ULN
Bilirubin Total (µmol/L)	-	34.2
BUN (mmol/L)	-	9.99
Creatinine (µmol/L)	-	176.8
Glucose (mmol/L)	2.78	9.99
Gamma GT (U/L)	-	3 x ULN
Potassium (mmol/L)	3	6
Magnesium (mmol/L)	0.51	1.07

v = volume, ULN = upper limit of normal

16.1.9.5 Vital signs and ECG – definition of clinically notable values

The following table shows the clinical notable criteria for vital signs.

Clinical notable criteria for vital signs

Vital sign parameter (unit)	Lower bound of clinically notable range	Upper bound of clinically notable range
Notable value considering newly occurring or worsening cases		
Systolic blood pressure (mmHg)	< 75	> 200
Diastolic blood pressure (mmHg)	< 40	> 115
Pulse rate (bpm)	< 40	> 130
Notable change from baseline		
Systolic blood pressure (mmHg)	≤ 90 and decrease from baseline by ≥ 20	≥ 180 and increase from baseline by ≥ 20
Diastolic blood pressure (mmHg)	≤ 50 and decrease from baseline by ≥ 15	≥ 105 and increase from baseline by ≥ 15
Pulse rate (bpm)	≤ 50 and decrease from baseline by ≥ 15	≥ 120 and increase from baseline by ≥ 15

The following table shows the clinical notable criteria for QTcF.

Clinical notable criteria for QTcF (Fridericia's formula)

ECG parameter (unit)	Clinically notable range
Notable value considering newly occurring or worsening cases	
QTc (ms)	> 450 (male)
QTc (ms)	> 460 (female)
QTc (ms)	> 500
Notable change from baseline	
QTc	30 – 60
QTc	> 60
Combination of QTc above a threshold and QTc increase from baseline above a threshold	
QTc (ms)	> 500 ms and increase from baseline > 60 ms

16.1.9.6 Statistical methodology and assumptions

In this section, the least squares mean (LSM) is estimated by the expected response for an “average” patient (with covariates set as weighted average of the covariates value in the population) based on the model (using OM option in PROC MIXED in SAS).

- **Mixed Model Repeated Measures (MMRM)**

The following MMRM ANCOVA will be used for trough FEV₁, ACQ-7, and other data:

Dependent variable = intercept + treatment + age group + region + baseline value + FEV₁ prior to inhalation + FEV₁ 15 to 30 min post inhalation + visit + treatment*visit + baseline value*visit + random effect of center nested within region + error.

The within-patient correlation will be modeled using an unstructured covariance matrix in the mixed model. The Kenward-Roger approximation will be used to estimate denominator degrees of freedom (Kenward and Roger, 1997).

For the primary analysis, if the model does not converge, data only up to Week 26 (i.e., Days 2 and 184) will be used (with unstructured covariance matrix). If still the model fails to converge, compound symmetry covariance matrix will be used. If the model still does not converge, the random effects of center will be removed. For the final analysis, if the model does not converge with unstructured covariance matrix, the compound symmetry covariance structure will be used. If still the model does not converge, the random effect of center will be removed. For both analyses, if the model converges after removing the random center effects, the original model without random center effects will be re-assessed. If the final model for the primary analysis converges without Week 52 data, only summary statistics will be provided for Week 52 data analysis.

Results will be presented with LSM and standard error (SE) for treatment effects and LSM, SE, associated two-sided 95% confidence interval, and two-sided p-value for all relevant treatment contrasts.

The combined effects of QMF149 (150/160 & 150/320 µg) and MF (400 & 800 µg) will be derived by weighting treatment groups equally.

In the analysis of eosinophil blood count, the covariates FEV₁ prior to inhalation and FEV₁ 15 to 30 min post inhalation will not be included in the MMRM.

- **Tipping point analysis for trough FEV₁ at Week 26**

As a sensitivity analysis to evaluate the impact of missing data, a tipping point analysis will be performed for the primary endpoint trough FEV₁ at Week 26. The delta-adjusting approach described in Ratitch et al (2013) will be used to find the tipping point, in a spectrum of conservative missing not at random (MNAR) assumptions, at which conclusions change from being favorable to QMF149 to being unfavorable. The basic idea is to first impute the missing Week 26 values using the multiple imputation (MI) method based on the MAR assumption. The imputed Week 26 values for the QMF149 arms are then adjusted by a delta value.

The endpoint is assumed to have a normal distribution at Day 2, Week 26 and Week 52. The primary analysis is performed on the delta-adjusted datasets to see if the conclusions change. If not, a larger delta is chosen and the process is repeated until the conclusion is overturned. The tipping point is the delta value which will cause the QMF149 vs. MF comparison on the primary endpoint to be no longer statistically significant. Different delta values are possible for QMF149 150/160 µg vs. MF 400 µg and QMF149 150/320 vs MF 800 µg. A series of analyses on a range of delta values will be performed to find the tipping point. For each delta value, the following steps will be performed.

1. Impute missing covariates (baseline FEV₁, FEV₁ prior to inhalation and FEV₁ 15 to 30 min post inhalation value) and missing values at Day 2 and/or Week 26 using the MI approach based on the fully conditional specification (FCS) method for 100 times and obtain 100 imputed datasets. Missing baseline FEV₁, FEV₁ prior to inhalation and FEV₁ 15 to 30 min post inhalation value will be imputed separately for each treatment group using a model with age group, geographic region, and the respective other covariates (baseline FEV₁, FEV₁ prior to inhalation and FEV₁ 15 to 30 min post inhalation value) as predictors. Missing Day 2 values will be imputed separately for each treatment group using a model with the imputed values of age group, geographic region, baseline FEV₁, FEV₁ prior to inhalation and FEV₁ 15 to 30 min post inhalation value as predictors. Missing Week 26 values will be imputed separately for each treatment group using a model with the imputed values of age group, geographic region, baseline FEV₁, FEV₁ prior to inhalation, FEV₁ 15 to 30 min post inhalation, and Day 2 value as predictors.
2. After the imputation obtained in above step, for subjects in the two QMF149 treatment arms only, make the imputed value at Week 26 worse by a value of delta (i.e., subtract delta from the imputed value at Week 26). Note: delta = 0 represents the standard missing at random (MAR) based MI.
3. The final multiply-imputed dataset where all missing values are filled will be analyzed (by imputed dataset) using a linear model with treatment, age group, geographic region, baseline FEV₁, FEV₁ prior to inhalation, and FEV₁ 15 to 30 min post inhalation as predictors of trough FEV₁ at Week 26.
4. The results for the treatment effect from the 100 datasets will then be combined using Rubin's rule. If the combined results does not change the conclusion (i.e., the QMF149 treatment effect is still statistically significantly superior to MF), a larger delta will be chosen and Steps 1-4 will be repeated using the datasets from Step 1 until the tipping point is found (when $p > 0.05$).

- **Logistic regression analysis**

The proportions of patients who achieve a clinically relevant improvement in ACQ-7 (i.e., decrease of ACQ-7 score of at least 0.5 from baseline) at the scheduled post-baseline visits will be analyzed using logistic regression. The following steps will be performed for imputation of missing ACQ-7 data and following logistic regression analysis:

1. First, missing ACQ-7 values (continuous) at Visit 202, 204, 207, and 214 will be imputed sequentially using the MI method under MAR assumption. Missing values will be imputed separately for each treatment group using a model with age group (12 to 17, or ≥ 18 years), region, baseline ACQ value, FEV₁ prior to inhalation, FEV₁ within 15 to 30 min post inhalation of salbutamol/albuterol, and previous post-baseline ACQ-7 values as predictors for 100 times.
2. Continuous ACQ values will be converted into binomial responses (1 = an improvement of at least 0.5, 0 = no such improvement) and generalized estimating equation (GEE) method will be used to analyze the dataset (by imputed dataset). The GEE model will include terms for treatment, age group (12 to 17, or ≥ 18 years), region, visit, and treatment-by-visit interaction as fixed effects, and baseline ACQ-7, baseline-by-visit interaction, FEV₁ prior to inhalation and FEV₁ within 15 to 30 min post inhalation of salbutamol/albuterol (components of SABA reversibility) as covariates.

Combining results from 100 copies of original dataset:

3. In the next step, results from each copy, obtained from GEE method will be combined for the inference using Rubin's rule. The SAS procedure PROC MIANALYZE will be used for combining the results considering the linear scale and then we will take exponential of combined result to obtain the odds ratio.

The combined effects of QMF149 (150/160 & 150/320 μg) and MF (400 & 800 μg) will be derived by weighting treatment groups equally.

The proportions of patients who achieve a clinically relevant improvement in AQLQ (i.e., decrease of AQLQ score of at least 0.5 from baseline) at the scheduled post-baseline visits (Visit 202, 204, 207, 210, and 214) will be analyzed using the same procedures as mentioned above for ACQ-7, except that baseline ACQ-7 is replaced by baseline AQLQ in all steps.

- **Linear Mixed Model Analysis of Covariance (ANCOVA)**

The following linear mixed ANCOVA model will be used for diary data summarized over 26 or 52 weeks:

Dependent variable = intercept + treatment + age group + region + baseline value + FEV₁ prior to inhalation + FEV₁ 15 to 30 min post inhalation + random effect of center nested within region + error.

Results will be presented with LSM and SE for treatment effects and LSM, SE, associated two-sided 95% confidence interval, and two-sided p-value for all relevant treatment contrasts.

- **Cox regression analysis**

A Cox proportional hazards regression model will be applied in time-to-event analyses to test the null-hypothesis $H_0: \lambda_{\text{QMF}}(t) / \lambda_{\text{Control}}(t) = 1$, where $\lambda(t)$ is the hazard function for the failure time of patients treated with QMF and the control group, respectively. The Cox regression

model will be stratified by age group (12 – 17, ≥ 18 years) and will include terms for treatment, region, history of asthma exacerbation in the 12 months prior to screening (Yes, No), FEV₁ prior to inhalation and FEV₁ within 15 to 30 min post inhalation of salbutamol/albuterol (components of SABA reversibility).

Results will be presented with adjusted hazard ratios for treatment group comparisons and associated 95% confidence intervals and two-sided p-values. P-values will be obtained from the Wald chi-squared statistic testing the null-hypothesis that the parameter estimate for the respective treatment effect is 0 (then the hazard ratio is $\exp(0) = 1$).

The combined effects of QMF149 (150/160 & 150/320 μg) and MF (400 & 800 μg) will be derived by weighting treatment groups equally.

No check for the validity of proportional hazards assumptions will be done.

- **Generalized linear model assuming a negative binomial distribution**

The annual rate of asthma exacerbations (by exacerbation category) will be analyzed using a generalized linear model assuming a negative binomial distribution. The model will include terms for treatment, age (12 – 17, ≥ 18 years), region, history of asthma exacerbation in the 12 months prior to screening (Yes, No), FEV₁ prior to inhalation and FEV₁ within 15 to 30 min post inhalation of salbutamol/albuterol (components of SABA reversibility).

The time at risk for a patient is defined as the duration of exposure in days + 1 day and the $\log(\text{time at risk in years})$ will be used as the offset variable in the model.

Treatment group ratios of exacerbation rates will be presented together with 95% confidence intervals and two-sided p-values.

The combined effects of QMF149 (150/160 & 150/320 μg) and MF (400 & 800 μg) will be derived by weighting treatment groups equally.

- **Van Elteren test**

The duration of asthma exacerbations (= the sum of days with an exacerbation, summarized by exacerbation category) will be analyzed for treatment group differences using the van Elteren test stratified for age (12 to 17, or ≥ 18), region and history of asthma exacerbation in the 12 months prior to screening (Yes, No).

Modified ridit scores (scores=modridit) represent the expected values of the order statistics of the uniform distribution on (0,1). Modified ridit scores are derived from rank scores. The 'Row Mean Scores Differ' statistic gives the relevant p-value of the test. To obtain p-values for pairwise treatment comparisons, the code above will be applied separately on datasets which include only the two treatments to be compared.

References

